**Table 1. Study Measures**

Feasibility and Acceptability Measures	
Measure	Definition
Study Participation Rate	Number of participants who consented to take part in the study divided by the number of patients approached. We will also document reasons for refusal to participate in the study.
Time to Recruit	Time required to attain the needed sample for each recruitment wave
Attendance	Attendance at each intervention session will be recorded.
Study Retention Rate	Number of participants in a study arm who remain in the study and maintain communication with study staff (regardless of session attendance) divided by the number of participants enrolled in the study.
Study Completion Rate	Number of participants who complete all assessments divided by the number of participants enrolled in the study arm.
Data Completeness	Percentage of questionnaires/study measures completed.
Program Acceptability	Acceptability of the intervention to participants as measured by agreement (on a 5-point likert scale) with different satisfaction measures.

Clinical Measures	
--------------------------	--

Hemoglobin A1c (HbA1c)  
 Body Mass Index (BMI)  
 BMI z-score

*\*When collecting clinical data from prediabetes or diabetes appointments, research team will document any changes to medications that impact glycemia and/or BMI.*

#### **Participant-Centered Measures**

Demographics  
 Patient-Reported Outcomes Measurement System Emotional Distress-Depression-Pediatric Item Bank (PROMIS)  
 Screen for Childhood Anxiety Related Emotional Disorders (SCARED-5)  
 Perceived Stress Scale (PSS-10)  
 Peds QL Generic Core Scales  
 Mindful Attention Awareness Scale (MAAS) – Adolescents  
 Difficulties in Emotion Regulation Scale (DERS)  
 L2B Program Questionnaires  
 Post-study guided interview:  
 1. What did you like about participating in this study?  
 2. What did you dislike about participating in this study?  
 3. What were your expectations from participating in this study?  
 4. Were those expectations met?

#### **Intervention:**

The MBI will be conducted in a virtual group setting by Zoom, with a target size of 8-12 participants. Groups may vary in size based on session attendance.

***Mindfulness-based intervention.*** The MBI will follow the Learning to BREATHE (L2B) curriculum. L2B is a manualized 12-week curriculum that teaches a variety of mindfulness skills including breath awareness, body scanning, mindful eating, sitting meditation, loving kindness practice, and mindful movement. Weekly group sessions will last 45-60 minutes. Participants will be invited to engage in daily practice of mindfulness skills (home practice).

**Table 2. Learning 2 Breathe Curriculum**

Session	Mindfulness Theme	Mindfulness Topic	Mindfulness Practice
1	Listen! Your body is trying to tell you something.	Define mindfulness	Body scan (short version)
2	Listen! Your body is trying to tell you something.	Mindfulness vs automatic pilot	Body scan (long version)
3	Thoughts are just thoughts.	What thoughts are like A common way to handle certain thoughts	Mindfulness of thoughts
4	Thoughts are just thoughts.	How thoughts affect us	Mindfulness of thoughts

5	Surf the wave of your emotions.	Universality of emotions Emotions and the mind-body connection	Find the feeling (short version)
6	Surf the wave of your emotions.	A common way to handle certain emotions	Surfing the waves of emotions plus gratitude
7	Attention to body, thoughts, and feelings is good stress management.	Basic concepts about stress Universality of stress	Mindful movement
8	Attention to body, thoughts, and feelings is good stress management.	Effects of chronic stress	Mindful movement
9	Learn to be kind to yourself and others	Basic concepts about the brain Practicing mental habits Ways we practice kindness or meanness to ourselves	Loving kindness meditation
10	Learn to be kind to yourself and others	Cultivating well-being	Person just like me
11	Habits for a healthy mind.	Program take-away	Participant choice
12	Habits for a healthy mind.	Closing Ritual	Compassion practice

**Compensation:**

We will offer \$10, \$25, and \$40 gift cards for the completion of study surveys at baseline (B), the completion of the intervention (T1), and 12 months following the intervention (T2), respectively. We will offer a \$10 gift card per group session for attendance. Participants can earn up to \$195 in total. This is reasonable because the study encourages the practice of the skills outside of the group sessions.

## **6.0 Reporting of Adverse Events or Unanticipated Problems involving Risk to Participants or Others**

Adverse events will be monitored by the PI and co-investigators. As the participants will be receiving clinical diabetes care and the intervention does not involve a medical intervention or change in medical diabetes therapy, physical adverse events related to the study are not expected. Potential adverse events that could occur include breach of subject confidentiality, loss of privacy in the group setting, discomfort with taking the surveys, and discomfort with the mindfulness skills exercises. Confidentiality will be respected and kept secure as described in section 9.0. Participants will be advised that they do not have to take a survey or answer a question if it causes them discomfort. Participants will be advised that they do not have to participate a particular mindfulness exercise if it causes them discomfort. The group covers topics on thoughts and feelings. If a group member discloses suicidal ideation, the facilitator will administer the Ask Suicide Risk Screening Questions (ASQ) directly after the group session in a one-on one setting to identify the appropriate triage steps. If there is an immediate threat to the participant's safety as indicated by the ASQ, they will be referred to the emergency room for evaluation. The research team will report suicide ideation to the participant's parent or guardian as well as the diabetes social worker. Each event will be handled individually. Adverse events or unanticipated problems involving risk to the participants or others will be reported according to IRB standard operating procedures. If the adverse event represents an unanticipated problem and requires changes to the research protocol, the informed consent process or document, or other corrective actions to protect the safety, welfare, or rights of subjects or others, it will be reported to the IRB using the Prompt Reporting Form within five business days of the investigator becoming aware of the event.

## **7.0 Study Withdrawal/Discontinuation**

The research team will terminate the involvement of a given participant in the research study if they request to stop participating. The criteria which would result in removal from the study are if they request to withdraw from the study or if there has been no communication with the participant in the first two weeks of the study.

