### Data Collection

**Process Measures:** Intervention fidelity will be assessed with a checklist of session content to ensure that the facilitator is delivering the intervention as intended. Facilitators will follow the manualized curriculum and scripts for mindfulness skills practice.

**Feasibility and Acceptability Measures:** Feasibility and acceptability measures include study participation rate, time to recruit, attendance, study retention rate, study completion rate, data completion, and program acceptability.

**Participant Measures:** Participants will be emailed a link to complete surveys in REDCap. Surveys will be completed at baseline (B), following completion of the MBI at 12-weeks (T1), and at the 12 month follow up (T2). Participants may complete follow-up surveys (12-weeks and 12 months) up to 1 month after the designated time point. A guided interview will also be performed at 12-weeks to receive feedback about the participants' experiences in the study.

Clinical data (HbA1c, BMI, and BMI z-score) will be collected at baseline and at each standard clinical prediabetes or diabetes appointment up to 12 months after the intervention.

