## **8.0 Statistical Considerations**

Anticipated statistics for this study will be a combination of descriptive statistics and quantitative statistics. For our primary outcomes, we will examine retention and acceptance, as assessed by overall program attendance, program acceptability, and qualitative interviews. Descriptive statistics will include sex, ethnicity, and survey results at B, T1, and T2.

This study includes a post-intervention group guided interview at 12-weeks. The facilitator will ask the group for feedback about the intervention with the following questions: 1) What did you like about participating in this study? 2) What did you dislike about participating in this study? 3) What were your expectations from participating in this study? 4) Were those expectations met?

A paired t test will be used to compare variables of an individual at baseline and at the end of the study (pre/post), including HbA1c, BMI, BMI z-score, and survey results.

This is a pilot feasibility study, therefore there are no data currently available to accurately calculate power. There are no similar studies to substitute such data.

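### Removal from the study for no communication in the first two weeks risks avoidable, selective loss of routine HbA1c and BMI data, and attendance has no all-enrolled denominator to guard against the same exclusion

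*Combined protocol and SAP*

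**What the plan says.** Section 7.0 gives two grounds for removal in one sentence. "The criteria which would result in removal from the study are if they request to withdraw from the study" is the first, and the second applies "if there has been no communication with the participant in the first two weeks of the study". Both lead to the same consequence. The section does not separate stopping the group sessions from stopping data collection, and it does not say what happens to data already held.

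Section 5.0 (Data Collection) has survey links emailed for baseline, 12 weeks (T1) and 12 months (T2). The clinical values (HbA1c, BMI, BMI z-score) "will be collected at baseline and at each standard clinical prediabetes or diabetes appointment up to 12 months after the intervention".

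For the primary outcomes, Section 8.0 states that "we will examine retention and acceptance, as assessed by overall program attendance, program acceptability, and qualitative interviews". In Table 1, the whole entry for attendance is that "Attendance at each intervention session will be recorded". The neighbouring measures do have a base: retention counts those still in communication, "regardless of session attendance) divided by the number of participants enrolled in the study", and completion is the "Number of participants who complete all assessments divided by the number of participants enrolled in the study arm".

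Section 8.0 plans paired t tests of baseline against end of study for HbA1c, BMI, BMI z-score and the surveys. No analysis population or missing-data rule is stated.

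**The concern.** Two consequences follow from the removal rule, and they should be kept apart.

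**Data loss.** A participant who is silent at the start has not withdrawn. If removal means what it ordinarily means, that person gets no T1 or T2 link and the chart is no longer abstracted. Yet the clinical values arise in usual care, whether or not the participant attends a session or answers a message. A paired test uses only people with both values, so the rule would shrink the pre/post sample and tilt it toward the engaged. The people lost also matter to Aim 2, which seeks factors that hinder uptake.

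**Attendance.** Attendance is the first assessor that Section 8.0 names for the primary outcomes, and it is the one without a denominator. Those removed are, by the rule's own definition, the least engaged. If the attendance figure is computed on whoever remains, it describes a group already filtered for engagement. In a feasibility study that figure informs whether and how to proceed to a larger trial.

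**Working it through.** The plan states no attendance rate, removal rate, power or effect size, so there is no figure of its own to reproduce. The documents supply a recruitment aim of 50 with a goal of at least 20 completing (Section 4.0), and 12 weekly sessions (Section 5.0, Intervention). Everything else below is an assumption.

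**Attendance.** Let N be the number enrolled, k the number removed under the two-week rule with no session attended, and a the mean attendance among those kept.

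- Attendance over all enrolled = a × (N − k)/N
- Overstatement if the k are left out = a × k/N, or a factor of N/(N − k)

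With N = 50 and a = 75% (assumed):

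| k removed (assumed) | Among those kept | Over all enrolled | Difference | Factor |
|---|---|---|---|---|
| 0 | 75% | 75% | 0 | 1.00 |
| 5 | 75% | 0.75 × 45/50 = 67.5% | 7.5 points | 50/45 = 1.11 |
| 10 | 75% | 0.75 × 40/50 = 60% | 15 points | 50/40 = 1.25 |
| 15 | 75% | 0.75 × 35/50 = 52.5% | 22.5 points | 50/35 = 1.43 |

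Over a wider range, with a from 60% to 80% and 10% to 40% removed, the difference runs from 0.60 × 0.10 = 6 points to 0.80 × 0.40 = 32 points. It is zero if nobody is removed or if all enrolled form the denominator.

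**Retention and completion.** Both divide by participants enrolled. For example, 20 completers of 50 enrolled is 40% whatever the number removed. It would read 20/40 = 50% with 10 removed only if the stated denominator were not followed.

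**Pre/post comparison.** The 95% half-width for a mean paired change, in SD units of the change, is t(0.975, n − 1)/√n. With illustrative pair counts:

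| Pairs n | Half-width |
|---|---|
| 50 | 0.284 SD |
| 40 | 0.320 SD |
| 35 | 0.344 SD |
| 30 | 0.373 SD |

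So losing 10 of 50 pairs widens the interval by 0.320/0.284 − 1, about 13%. This supposes that every lost pair would otherwise have been complete, so it is an upper limit for that number removed. The selection toward engaged participants cannot be sized from the documents.

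**The case against.** The strongest reply is that the plan states neither harm.

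- Section 7.0 says only that the participant is removed. That surveys and abstraction then stop is an inference.
- No text tells analysts to drop removed participants from attendance. The enrolled denominators for retention and completion in the same table could suggest that all enrolled is the intended base.
- The losses would stay visible. Retention requires continued communication, so early non-communicators count against it, and Section 11.0 has attrition summarised quarterly.
- The rule may catch few people.
- The pre/post comparison is exploratory and has no comparator, and people who never started received no intervention. Including them changes the question as well as the sample.
- People who do not communicate may not answer emailed surveys, and continued abstraction depends on consent wording that is not in the review copy.

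Most of this stands as a limit on the claim. It makes the inflation conditional, confines the clearest avoidable loss to chart data, and makes a consent check part of the fix. It does not remove the point. Non-contact is not withdrawal of consent, the rule as worded gives both the same consequence, and staff following it would most naturally stop collecting. Results for those who engaged can still be reported separately, which answers the objection about the changed question.

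**Conclusion.** The point holds in a limited form. The removal rule, on its natural reading, gives up routine HbA1c and BMI data that could be had without contact, and it does so selectively. Attendance can be overstated by a factor of N/(N − k), because Table 1 does not fix its denominator. The illustration of 67.5%, 60% or 52.5% against 75% rests on an assumed 50 enrolled, an assumed attendance among those kept, an assumed 5, 10 or 15 removed, and no sessions attended by those removed. The actual size is unknown.

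Four stronger readings are tempting, and the documents do not support them:

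- *That attendance is inflated.* This happens only if removed participants are excluded, and the plan is silent on that.
- *That retention and completion are inflated too.* Their stated denominators are the enrolled.
- *That any two-week silence triggers removal.* The rule covers only the first two weeks of the study.
- *That the plan expressly ends follow-up on removal.* It does not say so, although the wording points that way.

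**What to change.** **Section 7.0.** Reword so that no communication in the first two weeks is recorded as *not engaged* and does not by itself end data collection. Routine HbA1c, BMI and BMI z-score continue to be abstracted and T1 and T2 survey links continue to be sent, within the existing consent and unless consent is withdrawn.

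**Table 1.** Define attendance as sessions attended out of 12 for every enrolled participant, with 0 for each unattended session, and summarise it over all enrolled.

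**Section 8.0.** Report attendance and pre/post change among those who engaged as secondary, labelled as such.

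**Cost.** A protocol amendment, a check that the consent wording covers continued abstraction, and slightly more abstraction work. The attendance figure will be less favourable if anyone is removed early, and the main pre/post estimate will include participants who received little or no intervention. Survey recovery from this group may be low, so the gain is mainly in the chart data.

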## **8.0 Statistical Considerations**

Anticipated statistics for this study will be a combination of descriptive statistics and quantitative statistics. For our primary outcomes, we will examine retention and acceptance, as assessed by overall program attendance, program acceptability, and qualitative interviews. Descriptive statistics will include sex, ethnicity, and survey results at B, T1, and T2.

This study includes a post-intervention group guided interview at 12-weeks. The facilitator will ask the group for feedback about the intervention with the following questions: 1) What did you like about participating in this study? 2) What did you dislike about participating in this study? 3) What were your expectations from participating in this study? 4) Were those expectations met?

A paired t test will be used to compare variables of an individual at baseline and at the end of the study (pre/post), including HbA1c, BMI, BMI z-score, and survey results.

This is a pilot feasibility study, therefore there are no data currently available to accurately calculate power. There are no similar studies to substitute such data.

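### The 12-week interview, one of three sources for the primary outcome, is put to the whole group by the facilitator and asks about the study rather than the mindfulness sessions

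*Combined protocol and SAP*

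**What the plan says.** Section 8.0 says of the primary outcomes that "we will examine retention and acceptance, as assessed by overall program attendance, program acceptability, and qualitative interviews". It then sets the format: "This study includes a post-intervention group guided interview at 12-weeks", and the person asking: "The facilitator will ask the group for feedback about the intervention with the following questions: 1) What did you like about participating in this study". The second question is "What did you dislike about participating in this study". The third asks what participants expected from taking part in the study, and the fourth whether those expectations were met. The same four questions are listed under Participant-Centered Measures in Section 5.0.

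The Data Collection part of Section 5.0 gives the interview's purpose in other terms: "A guided interview will also be performed at 12-weeks to receive feedback about the participants' experiences in the study". The same part describes a fidelity checklist "to ensure that the facilitator is delivering the intervention as intended", which identifies the facilitator as the person running the sessions.

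Table 1 defines Program Acceptability separately: "Acceptability of the intervention to participants as measured by agreement (on a 5-point likert scale) with different satisfaction measures". Attendance is recorded at each session. On payments, the Compensation text says: "We will offer a \$10 gift card per group session for attendance. Participants can earn up to \$195 in total".

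**The concern.** Two features of the interview weaken it as evidence on acceptance.

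- **Who asks, and where.** Adolescents aged 12 to 18 are asked what they disliked by, it appears, the person who taught them for 12 weeks, with their peers listening. That setting discourages criticism. Nothing in the plan offsets it: there is no independent interviewer and no private route for these open questions.
- **What is asked.** The stated target is the intervention, but the questions name the study. A participant may answer about the sessions, the surveys, the gift cards or all three, and the analyst cannot tell which.

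Section 2.0 says the pilot should identify what supports or interferes with uptake and sustained use, to help plan later trials. These are the only open questions to participants that the plan sets out. If criticism is muted, or cannot be tied to the sessions, the pilot loses some of its most useful information.

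**Working it through.** The plan states no acceptability target, scoring rule or power figure tied to the interview, so there is no figure to reproduce. The check sets the relevant texts side by side.

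**1. Is the interview part of the primary outcome?** Yes. Section 8.0 names it as one of three sources, beside attendance and program acceptability.

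**2. Is the interviewer the person who delivered the sessions?** Probably. Section 5.0 uses the word facilitator for the person delivering the intervention, Section 6.0 uses it for the session leader who responds to a disclosure in the group, and Section 8.0 uses it for the interviewer. No other interviewer is named. Section 5.0 also uses the plural, and no sentence says that each group is interviewed by its own session leader. This is a strong inference, not a stated fact.

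**3. Which sources does this reach?**

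| Source | How obtained | Affected by the interview format? |
|---|---|---|
| Attendance | Recorded at each session | No |
| Program acceptability | 5-point agreement with satisfaction items | Not as defined |
| Qualitative interview | Facilitator asks the group | Yes |

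Section 5.0 sends surveys by emailed REDCap link, so the Likert items are probably answered individually. The plan does not state their route.

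**4. Do the questions match their target?** Section 8.0 wants feedback on the intervention. Questions 1, 2 and 3 ask about participation in the study; question 4 refers back to question 3. So three of the four name the study, and the fourth inherits that wording.

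**5. What else does the study contain?** Surveys at three time points, and payments. Maximum payment = 10 + 25 + 40 + 12 × 10 = $195, which reproduces the stated total. The session payments are 12 × 10 = $120, or 120/195 = 62% of it. Payments could raise liking. Surveys could raise disliking, and Section 6.0 lists discomfort with them as a possible adverse event. The direction of the mixture is not fixed.

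**6. How many accounts result?** With the completion goal of two groups of 10 in Section 4.0, one interview per group gives 2 conversations; an individual question would give up to 2 × 10 = 20 responses. The 2 follows from that goal and is not a fixed count. If all 50 recruits started in groups of the target size of 8 to 12, there would be 5 or 6 groups (50/12 = 4.2; 50/8 = 6.3).

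**7. Can the bias be sized?** No. The plan gives no method for coding the interviews and no rule for combining them with the other two sources.

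**The case against.** The strongest reply is that acceptability does not rest on the interview. The plan has a separate Likert measure, lists L2B program questionnaires and counts attendance. A reader might infer from the facilitator's role that the primary acceptability result as a whole is biased upward. The documents do not support that: two of the three sources are not defined through the interview, and for the third they show a risk, not an established bias. This part of the reply stands. It does not make the other sources a full safeguard, because attendance is itself paid and the route of the Likert items is unstated.

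A reader might also infer that the study wording inflates approval because praise for gift cards would count as praise for mindfulness. That does not follow, since surveys can pull the other way and a dislike question is asked outright. The defect is loss of specificity.

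Some study-level feedback is also legitimate: Section 2.0 includes adherence to the study protocol among the primary outcomes, and Section 5.0 describes the interview as covering experiences in the study. That is a reason to ask about both, separately. It does not remove the mismatch within Section 8.0.

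Finally, a group interview is an accepted qualitative choice, and asking about expectations only afterwards is a matter of preference in a pilot. Nothing in the plan promises one interview answer per participant, so the group format contradicts nothing. These points stand, and are why the group discussion should be kept.

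**Conclusion.** The concern holds for the interview component only. That component is exposed to socially desirable answers, probably favourable, and no safeguard is described. Separately, its questions do not isolate the intervention, with no predictable direction of error. Neither effect can be sized from the documents.

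The conclusion rests on two assumptions. The first is that the interviewer is the person who delivered that group's sessions. If someone else was intended, the exposure is smaller, and the text should say so. The second is that the Likert items are answered individually through REDCap. If the facilitator instead collected them in the group, the same exposure would reach that measure too.

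This is an inexpensive improvement to a primary-outcome source. It does not invalidate the feasibility assessment.

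**What to change.** In Section 8.0 and in the question list under Participant-Centered Measures:

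1. Reword the questions to name the mindfulness group sessions, and ask about study procedures (surveys, gift cards) in a separate question.
2. Add the like and dislike questions as individual free-text items in the 12-week REDCap survey, not visible to the facilitator, and report them alongside the group interview.
3. Where an existing team member who did not deliver the sessions is available, have that person lead the group discussion. The documents do not establish that there is one, so steps 1 and 2 should not wait for this.
4. Optionally, ask about expectations in the baseline survey and whether they were met at 12 weeks.

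The cost is a minor amendment and a few more items in surveys already being sent; no visit is added. Typed answers tend to be shorter than spoken ones, so the group discussion stays and the written items supplement it.

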## **4.0 Enrollment**

We aim to recruit 50 individuals with the goal of at least 20 participants to complete the study (two groups of 10 participants).

**Recruitment Sites:** Diabetes care providers see patients in an outpatient setting at Riley Specialty Care at IU Health Methodist in Indianapolis, Indiana. Additional outreach clinics available for participant recruitment include Riley Specialty Care at Riley Outpatient Center, IU North, Bloomington, Fort Wayne, and South Bend.

**Recruitment Procedures:** Eligible patients will be recruited in one of the following ways: 1) health care providers will identify eligible adolescents during clinic visits, 2) a letter will be mailed to patients referred for prediabetes or type 2 diabetes who have been seen in one of our clinics within the last 12 months, or 3) a member of the research team will call eligible patients. The letter and phone call scripts are provided in separate documents.

**Consent Procedures:** When a family indicates interest, a member of the research team will initiate contact with the parent or guardian at the end of a clinic visit (if time allows) or by phone. The team member will describe the study, assess eligibility, and answer questions. If the adolescent (and guardian) is willing to participate in the study, the consent process and baseline questionnaires will be completed virtually. The consent process will be based in REDCap. If a family declines participation, they will be asked if they would like to complete the study declination form. This will help to understand reason for disinterest in a MBI.

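### The only test of change is a paired t test to an unnamed end point: name T1-B and T2-B, model all survey values, and fix the clinic-value rule before extraction

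*Combined protocol and SAP*

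**What the plan says.** In the combined protocol and SAP, section 8.0 gives one inferential method for change: "A paired t test will be used to compare variables of an individual at baseline and at the end of the study (pre/post". It applies to HbA1c, BMI, BMI z-score and the surveys. T1 and T2 appear in that section only for description: "Descriptive statistics will include sex, ethnicity, and survey results at B, T1, and T2".

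Data Collection (section 5.0) schedules surveys at baseline (B), 12 weeks (T1) and 12 months (T2), and adds: "Participants may complete follow-up surveys (12-weeks and 12 months) up to 1 month after the designated time point". The Compensation paragraph dates T2 as "12 months following the intervention (T2". The 12-week interview is labelled "Post-study guided interview" in the list of participant-centered measures, whereas section 8.0 states: "This study includes a post-intervention group guided interview at 12-weeks".

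The clinical measures "will be collected at baseline and at each standard clinical prediabetes or diabetes appointment up to 12 months after the intervention". Section 4.0 says that consent and baseline questionnaires are done remotely, and that letters go to patients "who have been seen in one of our clinics within the last 12 months". Its target is 50 recruits with at least 20 completing. Section 9.0 mentions medical information gathered at screening and study visits but gives no timing. No missing-data method is stated.

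**The concern.** There are three gaps.

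1. **End point.** The test is tied to neither follow-up. The wording about the study's end points to T2, the last assessment. The pre/post label, and the use of a post-study label for the 12-week interview, leave T1 possible.
2. **Surveys.** Whichever follow-up is meant, a paired test discards anyone without both values and leaves the other follow-up without an estimate of change. A participant who returns B and T1 but not T2 adds nothing to a B-to-T2 test.
3. **Clinic values.** One participant may have several candidate values. The 1-month allowance covers surveys only, and nothing available sets a look-back limit, a follow-up window or a tie-break.

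Aim 2 is meant to give preliminary estimates for later trials, and section 8.0 says that no data exist for a power calculation. The changes and SDs from this pilot are therefore what a next trial would use, and the interval they describe should be known.

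**Working it through.** **No figure to reproduce.** The documents give no alpha, SD, correlation or return rate. The simulation results below rest on assumptions, which are stated.

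**Timing.** T1 is week 12 from session 1. With the Compensation anchor, T2 is week 12 + 52 = 64, and 64/12 = 5.3. Data Collection says only that the follow-up is at 12 months; counted from baseline that is week 52, and 52/12 = 4.3. The two readings of the end differ four- to fivefold in follow-up time.

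**Who enters the test.** 20/50 = 40%. Table 1 counts a completer only if every assessment is done, so the pairs for one scale can exceed the completers.

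**Surveys, random loss.** In SD units of the scale, SE(paired) = √(2(1−ρ)/n). With n = 20 this is √(1.0/20) = 0.224 at ρ = 0.5 and √(0.6/20) = 0.173 at ρ = 0.7. Simulated SEs, paired then model, by T1 return:
- ρ = 0.5: 0.228 to 0.213 (73%) and 0.226 to 0.212 (50%), reductions of 6.6% and 6.2%.
- ρ = 0.7: 0.174 to 0.165 (73%) and 0.179 to 0.171 (50%), reductions of 5.2% and 4.5%.

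A repeat run gave about 3-8%. Neither method is biased.

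**Surveys, loss following the observed change.** Assumptions: 50 enrolled, no true change, exchangeable correlation 0.5-0.7, random T1 loss, and T2 loss among T1 responders depending on the B-to-T1 change (logit slope 0.5-1.0 per SD).

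| T1 return | B-T2 pairs | Paired bias (SD) | Paired type I error |
|---|---|---|---|
| 73% | 20 | 0.07-0.19 | 6-13% |
| 60% | 20 | 0.05-0.14 | 6-9% |
| 50% | 20 | 0.03-0.09 | 5-7% |
| 44% | 20 | 0.01-0.04 | 5% |
| 80% | 30 | 0.04-0.10 | not reported |
| 66% | 30 | 0.01-0.04 | not reported |
| 90% | 40 | 0.02-0.05 | not reported |

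Model bias was at most 0.01 throughout. The paired bias shrinks as T1 return falls because fewer people are then selected out between T1 and T2: 0.73 × 50 = 36.5 T1 responders for 20 pairs, against 0.44 × 50 = 22.

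**Surveys, loss following the unobserved B-to-T2 change.** The model leaves 68-72% of the bias; for example 0.218 becomes 0.150, and 0.150/0.218 = 69%.

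**Type I error of the model** (Kenward-Roger, 20 pairs): 4.9-7.4%. When loss follows the T1 level it is 5.4-7.4%, against 4.6-5.9% for the paired test.

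**Clinic values, limits.** If the last value is 0-52 weeks old at session 1, change to T1 spans 12 to 52 + 12 = 64 weeks, and change to T2 spans 64 to 52 + 64 = 116 weeks.

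**Clinic values, spread.** Assumptions: visits every 13 or 26 weeks (±3), end = last visit by week 64.
- 25-50% letter recruits with a baseline value uniformly 0-52 weeks old: 5th-95th percentile 53-104 weeks (SD 12-15) with 13-weekly visits and 49-99 weeks (SD 15-16) with 26-weekly visits.
- Letter recruits on the same visit schedule before session 1 as after it: 53-70 weeks (SD 5.2) and 49-81 weeks (SD 13.0).
- With no letter recruits, 26-week windows change the SD from 5.2 to 5.2 and from 13.0 to 12.8.

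**A T1 clinic window centred on week 12.** With weeks 1-25, 46-50% of the selected values fall before week 12, while the programme is still running.

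**The case against.** The strongest reply is that T2 is the natural reading, so one clarifying line would do, and that these are preliminary secondary outcomes of an unpowered single-group pilot for which a paired t test is adequate. The return rates, loss mechanism and correlations are assumed. The largest bias in the table (0.19 SD) is below the paired test's own standard error at ρ = 0.5 (0.23). The model's small bias follows from simulating loss on an observed quantity, and its type I error can be slightly worse. Much of this stands: the survey bias is conditional, and the efficiency gain is modest. It does not answer the loss of T1 data from participants without T2, or the follow-up left untested.

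On clinic values, a reader might infer that HbA1c and BMI changes will mix intervals of up to 104 weeks or more. The documents do not support that. Being seen within 12 months is an outer limit for mailing letters, not the age of a value. Data Collection lists baseline collection separately from routine appointments, section 9.0 refers to screening and study visits, and neither the letter share nor the visit frequency is given. The wide percentiles are an upper illustration. What stands is that no available section gives a selection rule.

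A reader might also infer that completers-only results will be biased, or that a mixed model would cure any loss. Neither follows: under random loss there is no bias, and under loss on unobserved change most of it remains.

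**Conclusion.** The concern holds as a worthwhile improvement to the Aim 2 analysis. The end point needs naming, although T2 is the likelier intent. For surveys, one model on all B, T1 and T2 values improves on the stated test: the SE is about 3-8% smaller with 20 pairs under random loss, and a bias of about 0.03-0.19 SD is removed at 50-73% T1 return if loss follows the observed B-to-T1 change. That second gain is near zero at lower T1 return and rests on a loss pattern that the documents neither state nor exclude. For HbA1c, BMI and BMI z-score the gap is a missing selection rule. Its effect on the interval may be small: if letter recruits keep the assumed visit schedule, the SD is 5.2 or 13.0 weeks and windows change little. The primary feasibility and acceptability results are not affected.

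**What to change.** 1. State two contrasts, T1-B and T2-B, each with a 95% CI, and give the anchor of T2.
2. For each survey score, estimate both from one linear mixed model on all available B, T1 and T2 values: visit as a factor, unstructured covariance, REML with Kenward-Roger. State the missing-at-random assumption.
3. Keep the paired t test as a completer sensitivity analysis, and report the B-to-T1 change in participants with and without T2.
4. For HbA1c, BMI and BMI z-score, fix a baseline look-back limit and a T2 window before any values are extracted. Take any T1 clinic value only from visits at or after the end of the 12-week programme. Tabulate actual days from session 1.

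**Cost.** A paragraph of text and a few lines of code, with no new data. Reporting is slightly more complex, and the model's type I error is about 5-7% at 20 pairs. Windows lose some clinic pairs. In the illustration with 25-50% letter recruits and baselines up to 52 weeks old, a 26-week look-back with a T2 window of weeks 38-64 leaves 13-30% without a B-T2 pair. With 13-week windows and 26-weekly visits, only 9-10% would have one, so the widths should reflect the clinics' actual visit spacing. None of this separates an intervention effect from natural change without a control group.
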